## SUMMARY AND TRIAL OVERVIEW

The severe acute respiratory syndrome coronavirus 2 (SARS-CoV-2), the virus responsible for coronavirus disease 2019 (COVID-19), is associated with a high incidence of acute respiratory distress syndrome (ARDS) and death. Aging, obesity, diabetes, hypertension and other risk factors associated with abnormal lipid and carbohydrate metabolism are risk factors for death in COVID-19.

Recent studies suggest that COVID-19 progression is dependent on metabolic mechanisms. Moreover, gene expression analyses in cultured human bronchial cells infected with SARS-CoV-2 and lung tissue from patients with COVID-19, indicated a marked shift in cellular metabolism, with excessive intracellular lipid generation. In this cell culture system, fenofibrate (a widely available low-cost generic drug approved by the FDA and multiple other regulatory agencies around the world to treat dyslipidemias) at concentrations that can be achieved clinically, markedly inhibited SARS-CoV-2 viral replication. Fenofibrate also has immunomodulatory effects that may be beneficial in the setting of COVID-19. The aim of this trial is to assess the clinical impact of fenofibrate (administered for 10 days) to improve clinical outcomes in patients with COVID-19.

The **primary endpoint** of the trial will be a global rank score that ranks patient outcomes according to 5 factors: (1) time to death (ranked from shortest to longest, up to 30 days post-randomization), (2) the number of days supported by mechanical ventilation (invasive or non-invasive) or extracorporeal membrane oxygenation (until hospital discharge, up to 30 days post-randomization, ranked from longest to shortest); (3) The inspired concentration of oxygen/percent oxygen saturation ( $\text{FiO}_2/\text{SpO}_2$ ) ratio area under the curve (until hospital discharge, up to 30 days post-randomization, ranked from highest to lowest); (4) For participants enrolled as outpatients who are subsequently hospitalized, the number of days out of the hospital during the 30 day-period following randomization (ranked from lowest to highest); (5) For participants enrolled as outpatients who don't get hospitalized during the 30-day observation period, the modified Borg dyspnea scale (mean value of assessments at ~5, and ~10 and ~15 days).

**Secondary endpoints** will include:

- (1) Number of days alive, out of the intensive care unit, free of mechanical ventilation (invasive and non-invasive), extracorporeal membrane oxygenation (ECMO) or maximal available respiratory support in the 30 days following randomization.
- (2) A seven-category ordinal scale consisting of the following categories: 1, not hospitalized with resumption of normal activities; 2, not hospitalized, but unable to resume normal activities; 3, hospitalized, not requiring supplemental oxygen; 4, hospitalized, requiring supplemental oxygen; 5, hospitalized, requiring nasal high-flow oxygen therapy, noninvasive mechanical ventilation, or both; 6, hospitalized, requiring extracorporeal membrane oxygenation (ECMO), invasive mechanical ventilation, or both; and 7, death.
- (3) A global rank score similar to the primary endpoint, but using a more comprehensive COVID-19 symptom scale instead of the dyspnea Borg scale (Appendix 1).

**Exploratory endpoints** will include:

- (1) All-cause death.
- (2) Number of days alive and out of the hospital during the 30 days following randomization.
- (3) A global rank score similar to the primary endpoint, but built only with factors 1-4.

All primary analyses will be performed on an intent-to-treat basis.

## 1. BACKGROUND AND SIGNIFICANCE

The severe acute respiratory syndrome coronavirus 2 (SARS-CoV-2), the virus responsible for coronavirus disease 2019 (COVID-19), is associated with a high incidence of acute respiratory distress syndrome (ARDS) and death.

Recent studies suggest that COVID-19 progression is dependent on metabolic mechanisms. T2DM and hypertension have been identified as the most common comorbidities for other serious coronavirus infections, such as severe acute respiratory syndrome (SARS) and Middle East respiratory syndrome (MERS-CoV). Individuals infected with COVID-19 who developed ARDS and death have been characterized by older age and a higher prevalence of hypertension, diabetes, and cardiovascular diseases compared to those individuals with milder disease. Hyperglycemia and hyperlipidemia are also risk factors for acute respiratory distress in the setting of COVID-19. Indeed, patients with T2DM and the metabolic syndrome appear to have up to ten-times greater risk of death when they contract COVID-19.

Several experimental studies suggest a mechanistic link between abnormal metabolism and the severity of SARS-CoV-2 and other coronavirus infections. Palmitoylation of SARS-CoV spike proteins has been shown to be essential for virion assembly and for partitioning into detergent-resistant membranes and for cell-cell fusion. For other coronaviruses, lipid accumulation occurs upon infection. Recent gene expression analyses in cultured human bronchial cells infected with SARS-CoV-2 and lung tissue from patients with COVID-19, indicated a marked shift in cellular metabolism, with excessive intracellular lipid generation. Ehrlich *et al* studied the metabolic rewiring induced by SARS-CoV-2 infection in the transcriptional signature of primary bronchial epithelial cells, validating their results in lung biopsy samples of COVID-19 patients. This study reported a significant metabolic response in SARS-CoV-2 infected lungs, covering ~60% of the differentially expressed genes. This transcriptional signature was characterized by changes in metabolism and pathways of endoplasmic reticulum stress, including upregulation of glycolysis and dysregulation of the citric acid cycle, upregulation of fatty acid and cholesterol synthesis, and the suppression of fatty acid oxidation. Peroxisome proliferator-activated receptor-alpha (PPAR $\alpha$ ) inhibition was shown to be involved in abnormalities in lipid metabolism in these experiments.

In further cell culture experiments, the PPAR $\alpha$ -agonist fenofibrate (a widely available low-cost generic drug approved by the FDA and multiple other regulatory agencies around the world to treat dyslipidemias) at concentrations that are likely to be achieved clinically, reversed the metabolic changes induced by SARS-CoV-2, and inhibited viral production/replication. Treatment of SARS-CoV-2 infected cells with fenofibrate (concentration: 20  $\mu$ M) blocked phospholipid accumulation and increased glycolysis, reversing the metabolic effects of infection. Viral replication was effectively blocked, reduced by 3-log over 5 days period to below the assay detection limit, while cell viability was unaffected. Fibrates also appear to exert immunomodulatory effects that could be beneficial in the setting of COVID-19. PPAR- $\alpha$  activation by fibrates has been described to beneficially influence inflammation and experimental lung injury.

Whereas these pre-clinical studies suggest that fenofibrate could directly target host metabolic pathways to minimize virus replication and possibly suppress its pathogenesis in lung tissue, a well-designed and rigorously executed randomized controlled trial is urgently needed to assess the potential efficacy and clinical benefit of fenofibrate in COVID-19. Fenofibrate is a widely-available, generic and inexpensive drug with a proven track record of safety for other indications (i.e., dyslipidemia). If effective for COVID-19, this trial could have a major public health impact.

[figure not shown]
The aim of this randomized controlled trial is to assess the clinical impact of fenofibrate to improve clinical outcomes in patients with COVID-19.

## 2. STUDY DESIGN AND POPULATION

### 2.1. Overview of study design

This will be a prospective randomized controlled trial of fenofibrate therapy (administered for 10 days) among patients with COVID-19. A general overview of the trial design is shown in **Figure 1**. A schedule of events is shown in **Appendix 2**.

**Figure 1. General workflow of the trial**

\* According to the approved label/package insert for each particular preparation

### 2.2. Study Sites

The trial will be executed at several sites in several countries, including the USA and various Latin American countries. Prior to initiation of the research in each site, IRB approval will be obtained for each site, and Health Authority approval will be obtained as per each country's regulations. In each country, there will be a qualified national PI / sponsor for regulatory processes.

### 2.3. Study Population

We will enroll 700 subjects meeting the following criteria:

#### Inclusion Criteria

- (1) Age 18 years or older
- (2) A diagnosis of COVID-19, based on: (a) A compatible clinical presentation with a positive laboratory test for SARS-CoV-2, or (b) Considered by the primary team to be a Person Under Investigation undergoing testing for COVID-19 with a high clinical probability, in addition to

- compatible pulmonary infiltrates on chest x-ray (bilateral, interstitial or ground glass opacities) or chest CT.
- (3) Able to provide informed consent.
- (4) Fewer than 14 days since symptom onset.

**Exclusion Criteria:**

- (1) Known pregnancy or breastfeeding.
- (2) Estimated glomerular filtration rate (eGFR) <30 mL/min/1.73m^2 or undergoing dialysis (CKD stages 4-5).
- (3) History of active liver disease, cholelithiasis, uncontrolled hypothyroidism, or rhabdomyolysis (suspected or confirmed). Patients with a history of hypothyroidism receiving a stable dose of thyroid replacement therapy for at least 6 weeks, with a documented normal TSH (primary hypothyroidism) or free thyroxine (secondary or tertiary hypothyroidism) level at least 6 weeks after the last dose change will be considered eligible for enrollment.
- (4) Known hypersensitivity to fenofibrate or fenofibric acid.
- (5) Ongoing treatment with fenofibrate, clofibrate, warfarin and other coumarin anticoagulants, glimepiride, cyclosporine, tacrolimus.
- (6) Use of statins other than simvastatin, pravastatin or atorvastatin ≤40 mg/d or rosuvastatin ≤20 mg/d.
- (7) Prisoners/incarcerated individuals
- (8) Inability to read, write or no access to a smart phone, computer or tablet device.
- (9) Intubated patients.

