## **2.8. Concomitant Medication**

Participants will be treated by their clinicians, at their discretion, with standard of care medications for COVID-19 and associated comorbidities. Participants will be allowed to receive antiviral, immunomodulatory, or convalescent plasma. Since fenofibrate/fenofibric acid are well-known medications, enrollment in other clinical trials will be allowed as long as fenofibrate/fenofibric acid use is not an exclusion criterion for other trials.

We will remind inpatient clinicians to consider potential interactions with fenofibrate, particularly in patients who require *de novo* warfarin treatment (which should ultimately be guided by INR checks as per standard practice). We will also ask them to try avoiding the *de novo* use of medications that may interact with fenofibrate or fenofibric acid (colchicine, glimepiride, cyclosporine, tacrolimus, statins) unless clear indications exist in the absence of suitable therapeutic alternative agents; if glimepiride, cyclosporine or tacrolimus are required, we will discontinue the study medication. For colchicine, atorvastatin and simvastatin, we will ask clinicians to be mindful of a potential interaction, which is however, not anticipated to constitute a significant risk with only 10 days of treatment (see section on “Risks to study subjects”). If cholestyramine or colestipol are part of the medical regimen at baseline or during the period of study medication administration, we will ask participants to take the study medication at least 1 hour before or 6 hours after the bile acid binding resin to avoid a pharmacokinetic interaction (reduced absorption). For outpatients, we will ask participants to contact us if any new medication is initiated by their physicians during the treatment period, and we will establish a similar approach in communication with the prescribing clinician.

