## **2.10. Follow-up assessments**

For participants randomized as inpatients, daily assessments (via medical record review) will be performed to assess clinical status, with particular attention to the study endpoints (death, mechanical ventilation and the  $\text{FiO}_2/\text{SpO}_2$  ratio), until hospital discharge or 30 days (whichever is shortest). For participants discharged prior to 30 days-post randomization, a follow-up call will be performed at the ~30-day time point to assess vital and functional status, symptoms and major adverse events, including hospitalizations.

For participants randomized as outpatients or discharged within 24 hours of receiving the first dose of the study medication, participants will be called at approximately 5, 10, 15 and 30 days post-randomization, in order to assess vital and functional status, hospitalization status, the severity of dyspnea (via the modified Dyspnea Borg Scale, **Appendix 1**) and major adverse events. An effort will be made to make these assessments at the exact time points, but we recognize that this is often not possible due to work schedules and inability to get in touch with participants for various reasons. In these instances, we will make the assessments at time points that are as close as possible to the scheduled time points.

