### **8.2. Risks to study subjects**

All subjects will be adults able to give informed consent. Subjects will be enrolled regardless of sex, race or ethnicity, aiming to assure adequate representation of women and ethnic minorities. Children will not be enrolled.

The risks to study subjects are related to the potential side effects of the study intervention. The dose used in this trial is the starting dose for primary hypercholesterolemia and mixed dyslipidemia and is utilized as a chronic therapy, for months or years. We propose to administer this dose for only 10 days.

With chronic therapy, adverse reactions > 2% and at least 1% greater than placebo include abnormal liver blood tests (increased AST and ALT) increased creatine kinase (CPK), and rhinitis. Rhabdomyolysis have been reported in patients taking fenofibrate, but is considered extremely

rare, with <20 cases reported worldwide for fibrate monotherapy. Moreover, the median duration of therapy prior to rhabdomyolysis was 17.5 days. In the Fenofibrate Intervention and Event Lowering in Diabetes (FIELD) trial, 9,795 were randomized to fenofibrate or placebo for 5 years. This provided >8 million patient-days of observation in the active arm alone. In this trial, only 3 patients allocated to fenofibrate had rhabdomyolysis, which in each case fully resolved; this incidence was not significantly different than that of the placebo arm (1 case of rhabdomyolysis). The risk of rhabdomyolysis may be increased during co-administration with a statin, in renal failure, or hypothyroidism. Accordingly, we will exclude all patients with advanced renal dysfunction and those with a history of hypothyroidism.

Regarding statins, although there is an increase in reports of rhabdomyolysis with statin-fibrate combined therapy, this risk appears to be much higher when statins are combined with gemfibrozil than fenofibrate. In a meta-analysis of 6 trials including 1,628 subjects taking fenofibrate in combination with statin therapy, no case of myopathy or rhabdomyolysis was reported. This included data from the LCP-AtorFen trial, in which atorvastatin (40 mg/d) was administered alone or with fenofibrate for 12 weeks, as well as some studies with simvastatin (20 mg/d).

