
Given that we will only administer 10 days of therapy, we consider the risk of rhabdomyolysis, even in patients taking statins or colchicine, to be negligible. Nevertheless, as a precaution, we will exclude patients who are taking statins other than simvastatin and atorvastatin; similarly, we will exclude patients who are taking simvastatin or atorvastatin at doses >40 mg/d,

since doses >40 mg/d of these 2 drugs in combination with fenofibrate have not been specifically studied. Finally, we will ask site investigators to communicate any occurrence of rhabdomyolysis to the Principal Investigator, who in turn will immediately communicate them to the DSMB for a formal assessment (with unblinding of the DSMB if required). We will inquire about potential manifestations of rhabdomyolysis (particularly hemoglobinuria) in all data collection forms and the study medication will be discontinued immediately upon suspected or confirmed rhabdomyolysis.

Fenofibrate can increase serum transaminases and/or serum creatinine and periodic monitoring is recommended during chronic therapy. However, we will only utilize it for 10 days in this trial and will exclude patients with active liver disease or advanced renal disease. Therefore, the need for periodic monitoring does not apply for such as short treatment. Moreover, the mild increase in serum creatinine is not thought to be due to impaired true glomerular function, as measured by inulin clearance, the gold standard measure of renal function. This creatinine rise does not increase the risk of adverse renal outcomes or cardiovascular events, and is fully reversible upon discontinuation.

Fenofibrate increases cholesterol excretion into the bile, leading to risk of cholelithiasis. This is not anticipated to be a problem with 10 days of therapy, and our trial will exclude patients with a history of gallbladder disease. As recommended by the approved prescribing information, we will also exclude nursing mothers, and patients with known hypersensitivity to fenofibrate or fenofibric acid.

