Fenofibrate can also rarely cause allergic reactions and mild to moderate changes in blood cell counts. Pancreatitis has been observed (in post-marketing case reports) in people taking fenofibrate for dyslipidemia, but is an extremely rare occurrence. Of note, the overwhelming majority of these reports involved patients who had other, more strongly associated risk factors for acute pancreatitis and it is unclear whether and to what degree was fenofibrate causally involved. Moreover, the incidence of pancreatitis has been estimated to be very low (0.13 per 100 patient years on monotherapy and 0.16 per 100 patient years in combination with a statin) and such a complication is extremely unlikely with 10 days of therapy.

Drugs that exhibit significant interactions with fenofibrate include coumarin anticoagulants, immunosuppressants and glimepiride. We will exclude patients taking these medications.

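### Exclusion 5 names two fibrates but not the class, so a patient taking gemfibrozil or bezafibrate can be randomised and, in the active arm, given a second fibrate

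*Protocol*

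**What the plan says.** Exclusion 5 in Protocol section 2.3 rules out "Ongoing treatment with fenofibrate, clofibrate, warfarin and other coumarin anticoagulants, glimepiride, cyclosporine, tacrolimus". Within that one sentence the coumarins are covered as a class, while the fibrates are covered by two names only. Exclusion 6 concerns statins alone. Exclusion 4 names fenofibric acid, but only for hypersensitivity.

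Section 2.8 deals with interacting drugs started after enrolment. It asks clinicians to try to avoid several agents, none of them a fibrate, and makes three of them grounds for stopping: "if glimepiride, cyclosporine or tacrolimus are required, we will discontinue the study medication".

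Section 8.2 summarises the interactions that led to exclusions: "Drugs that exhibit significant interactions with fenofibrate include coumarin anticoagulants, immunosuppressants and glimepiride". Fibrates are absent from that list too. Gemfibrozil and bezafibrate do appear in section 8.2, but as comparators in the discussion of myopathy, not as excluded drugs. On rhabdomyolysis, the section concludes "we consider the risk of rhabdomyolysis, even in patients taking statins or colchicine, to be negligible".

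**The concern.** By listing clofibrate, exclusion 5 already treats at least one other fibrate as disqualifying. Leaving out gemfibrozil, bezafibrate and fenofibric acid therefore looks like an incomplete list and not a decision to allow them. Fenofibric acid is the clearest sign: it is one of the randomised preparations (section 2.5), yet a patient already taking it is not barred.

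What is at stake is safety. The reassurance in section 8.2 does not extend to two fibrates at once. Its case count is of "cases reported worldwide for fibrate monotherapy", its large trials test fenofibrate against placebo or on top of simvastatin, and its argument about statins rests on fenofibrate being unlike gemfibrozil. Exclusion 6 still admits patients on four statins within limits, so a patient on gemfibrozil plus simvastatin is eligible and may have fenofibrate added. The 10-day argument limits exposure to the study drug but not to the patient's own fibrate.

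Screening matters because later checks are limited. Section 8.2 states that "the need for periodic monitoring does not apply for such as short treatment", the schedule in Appendix 2 shows no laboratory tests after baseline, and for those enrolled as outpatients "participants will be called at approximately 5, 10, 15 and 30 days post-randomization". The eGFR and transaminase stopping rules in section 2.7 therefore depend on tests done in routine care.

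**Working it through.** **Text check.** The question is whether any visible text stops a patient who takes gemfibrozil or bezafibrate and meets the other criteria.

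| Place | What it covers | Bars another fibrate? |
|---|---|---|
| Section 2.3, exclusion 5 | Fenofibrate, clofibrate and listed non-fibrates | Only clofibrate |
| Section 2.3, exclusion 6 | Statins | No |
| Section 2.7, stopping rules | Renal function, rhabdomyolysis, urine colour, liver | No |
| Section 2.8 | Colchicine, glimepiride, cyclosporine, tacrolimus, statins, warfarin, bile acid resins | No |
| Section 8.2, interaction list | Coumarins, immunosuppressants, glimepiride | No |
| Appendix 3, US part | Preparation, dosing, baseline tests, consent | No |
| SAP | No eligibility text | No |

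There is no general exclusion based on investigator judgement or label contraindications. The patient passes exclusions 1 to 9 and is randomised 1:1 (section 2.5).

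**Consistency check.** Section 8.2 excludes simvastatin and atorvastatin above 40 mg/d because those doses have not been studied with fenofibrate, even though it regards the overall risk as negligible. It cites no study of two concurrent fibrates. The same standard would exclude them.

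**Scale.** The plan gives no figure to reproduce. The following is for orientation only.

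*Inputs from the documents:*
- 700 participants, 1:1, so 350 in the active arm.
- 10 days of treatment.
- From the FIELD trial, as reported in section 8.2: "only 3 patients allocated to fenofibrate had rhabdomyolysis", in more than 8 million active-arm patient-days.
- Power of 80% at alpha 0.0492 (section 7.1).

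*Assumptions with no source in the documents:*
- A proportion p of 0.1% to 2% of participants use an unlisted fibrate.
- The rhabdomyolysis rate on two fibrates is 100 times the FIELD rate.
- For power, these users show no treatment effect.

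*Background rate:* 3 / 8,000,000 = 3.75 × 10⁻⁷ per patient-day. This is an upper figure, since the denominator exceeds 8 million.

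*Active arm as a whole:* 350 × 10 = 3,500 treatment days, and 3,500 × 3.75 × 10⁻⁷ = 0.0013 expected cases.

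| Quantity | Formula | p = 0.1% | p = 2% |
|---|---|---|---|
| Users enrolled | 700p | 0.7 | 14 |
| Users in active arm | 350p | 0.35 | 7 |
| Days on two fibrates | 3,500p | 3.5 | 70 |
| Expected cases at 100 × FIELD rate | 3,500p × 3.75 × 10⁻⁵ | 0.00013 | 0.0026 |

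*Power:* the two-sided critical value at 0.0492 is 1.967, and 80% power corresponds to a noncentrality of 2.808. Diluting the effect by the factor (1 − p) gives power Φ(2.808(1 − p) − 1.967):
- p = 0.1%: Φ(0.838) = 0.799
- p = 2%: Φ(0.785) = 0.784

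**The case against.** The strongest reply is that the documents show no harm from the gap. The warnings about gemfibrozil and bezafibrate in section 8.2 concern their use with statins or colchicine, not with fenofibrate, and the protocol never says why clofibrate is listed. The prevalence and the 100-fold multiplier are assumptions, and even so the expected number of cases is close to zero. All of this stands. It sets the priority low but does not make the criterion complete.

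Safeguards also exist. Signs of rhabdomyolysis are asked about on every data collection form, which means daily for inpatients and at each scheduled call for outpatients. Suspected cases and red or brown urine stop the drug, and any case goes to the DSMB. Inpatient clinicians are reminded about interactions in general, and outpatients are asked to report new medicines. Severe renal impairment and uncontrolled hypothyroidism, which bear on the two non-drug risk factors that section 8.2 names, are excluded. These measures limit harm once exposure has begun, and the request to report new medicines partly covers a fibrate started later. None of them prevents enrolment of a patient already on another fibrate.

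Two limits of scope also stand. Only the active arm would receive a second fibrate. And Appendix 3 varies by country with only the US part shown, so other countries may have added a restriction.

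**Conclusion.** The gap is real in the universal criteria and the US appendix: the rule as written admits patients on gemfibrozil, bezafibrate or fenofibric acid. Confidence is high on the wording. The size of any safety consequence is unknown, because the documents give neither how many patients use these drugs nor the added risk from 10 days on two fibrates.

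The orienting figures show a very small expected effect even when the risk is multiplied by 100. They rest on the stated assumptions and on a rate from people with type 2 diabetes, which may not carry over to acute COVID-19. The effect on the primary result is negligible. This is an improvement to consider. It is worth making because it is cheap and brings the criterion into line with the protocol's own precaution on unstudied combinations.

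**What to change.** In exclusion 5, replace the two fibrate names with any fibrate, giving fenofibrate, fenofibric acid, gemfibrozil, bezafibrate and clofibrate as examples, and leave the rest of the list unchanged. In section 2.8, add any fibrate to the drugs whose start requires stopping study medication.

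The cost is one line in the exclusion list and the screening form, and one line in section 2.8. Under the assumed 0.1% to 2%, between 0.7 and 14 of 700 otherwise eligible patients would be turned away, and competitive enrolment (section 2.4) would replace them. Stopping study drug under section 2.8 need not lose outcome data, since section 2.7 keeps data collection going after discontinuation.
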